#### 10.2.5.1. Statistical Methodology Specification

Endpoint

 
• Ratio to baseline total IL-5 at Week 32
 

Model Specification

 
• Wilcoxon Rank Sum test stratified by baseline OCS dose (<math>0 \leq 20</math>mg/day and <math>>20</math>mg/day prednisone or equivalent) and region.
 

Model Results Presentation

 
• Number analysed in each treatment group.
 
• Median change from baseline at Week 32 in each treatment group.
 
• p-value for difference between treatments from Wilcoxon Rank Sum test.
 

Subgroup Analyses

 
• No subgroup analyses will be performed on this endpoint.
 

Sensitivity and Supportive Statistical Analyses

 
• No sensitivity analyses will be performed.
 

## 11. SAFETY ANALYSES

The safety analyses will be based on the Safety population, unless otherwise specified.

### 11.1. Adverse Events Analyses

Adverse events analyses including the analysis of adverse events (AEs), Serious (SAEs) and other significant AEs will be based on GSK Core Data Standards. Common AEs will be defined as AEs with frequency  $\geq 3\%$  (prior to rounding to nearest percent) in either treatment group.

The details of the planned displays are provided in [Appendix 10](#): List of Data Displays.

#### 11.1.1. Adverse Events of Special Interest

Adverse events of special interest (AESIs) reported by the investigator as systemic reactions (further categorised by the investigator as either allergic [type I hypersensitivity] or other systemic reactions and assessed against Sampson criteria for anaphylaxis) are collected via targeted eCRF within the study. Local injection site reactions are also collected via targeted eCRF within the study.

AESIs of potential opportunistic infections, malignancies, serious cardiac, vascular and thromboembolic (CVT) events and serious ischemic events will be identified from a list of relevant preferred terms maintained within a project level reference dataset created based on the MedDRA dictionary available at the time of DBF for this study. Further details of how relevant preferred terms are identified are given in the Program Safety Analysis Plan (PSAP).

Separate summary tables showing the number and percent of subjects with each type of AESI, broken down by preferred term will be created.

For each type of AESI a profile summary table will be produced containing information including, but not limited to, the number of occurrences of the event, event characteristics, time to onset, intensity, outcome and action taken.

The relative risk of each AESI between mepolizumab and placebo with 95% confidence intervals will also be presented.

Separate listings of AESIs identified by the investigator as anaphylaxis, allergic (type I hypersensitivity), other systemic reactions and local injection site reactions will be produced, as well as listings of potential opportunistic infections, malignancies, serious CVT events and serious ischemic events.

### 11.2. Clinical Laboratory Analyses

Laboratory evaluations including the analyses of Chemistry laboratory tests, Haematology laboratory tests and liver function tests will be based on GSK Core Data Standards. The details of the planned displays are provided in [Appendix 10](#): List of Data Displays.

A scatter plot of maximum ALT vs baseline ALT, and maximum ALT vs total bilirubin will be produced. In addition, if any liver stopping or liver monitoring events occur during the study, summaries of liver monitoring/stopping event reporting and hepatobiliary laboratory abnormalities will be produced.

### **11.3. Other Safety Analyses**

The analyses of non-laboratory safety test results including ECGs and vital signs will be based on GSK Core Data Standards, unless otherwise specified. The details of the planned displays are presented in [Appendix 10](#): List of Data Displays.

## **12. IMMUNOGENICITY ANALYSES**

### **12.1. Overview of Immunogenicity Analyses**

For the immunogenicity assessment, two types of anti-drug antibody (ADA) assays will be performed, a binding anti-drug antibody assay and a neutralizing antibody assay.

For the binding assay, there will be a three tiered analysis: screening, confirmation and titration. The screening assay produces a result of positive or negative relative to a screening cut point. Positive samples continue with the confirmation assay, which also produces a result of positive or negative relative to a confirmation cut point. For positive confirmation samples, a titre value will also be obtained to quantify the degree of binding in a titration assay and the sample will be tested with the neutralizing assay, which also reports results as positive or negative.

The binding ADA results at each visit will be categorised as negative, transient positive (defined as a single confirmatory positive immunogenic response that does not occur at the final study assessment) or persistent positive (defined as a confirmatory positive immunogenic response for at least 2 consecutive assessments excluding the screening visit, or a single result at the final study assessment). In addition, the highest post-baseline binding ADA confirmatory result obtained for a subject will be summarised. Subjects with both positive and negative results will be identified in the positive category. Summary statistics for the titre result by visit will also be presented.

A summary of adverse events by highest post-baseline binding ADA confirmatory result (as defined above) will be produced.

A summary of treatment emergent positive confirmatory binding ADA results in the subset of subjects who did not have a positive confirmatory binding ADA result prior to the dosing of study treatment will also be presented.

Neutralizing antibody assay results will be summarised by visit. In addition, the highest post-baseline neutralising antibody assay result during the treatment period of the study will be summarised, with subjects with both positive and negative results identified in the positive category.

Immunogenicity data will be listed for subjects with at least one positive screening binding assay.

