DIAGNOSTIC ASSESSMENTS AND OTHER CRITERIA

7. Clinical diagnosis of eosinophilic granulomatosis with polyangiitis (EGPA)

8. Malignancy:

- Subjects with a history of *or* current lymphoma
- Subjects with current malignancy or previous history of cancer in remission for less than 12 months prior to randomization (Visit 2). Subjects that had localized carcinoma (i.e., basal or squamous cell) of the skin which was resected for cure will not be excluded.

9. FIP1L1-PDGFR α Status: Subjects who test positive for the FIP1L1-PDGFR α fusion tyrosine kinase gene translocation.

Blood sampling is required for all subjects at screening (Visit 1) for this test unless the documented result is available.

10. Infection:

- Subjects with chronic or ongoing active infections requiring systemic treatment, as well as subjects who have experienced clinically significant infections due to viruses, bacteria, and fungi within 4 weeks prior to randomization (Visit 2).
- Subjects with a pre-existing helminthes infestation within 6 months prior to randomization (Visit 2).

11. Subjects with a known immunodeficiency (e.g., HIV), other than that explained by the use of OCS or other therapy taken for HES.

12. Other laboratory abnormalities: Evidence of clinically significant abnormality in the hematological, biochemical or urinalysis screen from the sample collected at screening (Visit 1), that could put the subject's safety at risk by participating in the

study, as judged by the investigator

CONCOMITANT MEDICATIONS

- | |
|--|
| 
13. Subjects who have previously received mepolizumab in the 4 months prior to randomization (Visit 2).
 
14. Subjects receiving any of the following:
 
 • Intravenous or subcutaneous corticosteroids in the 4-week period prior to randomization (Visit 2). • Any other monoclonal antibodies within 30 days or 5 half-lives, whichever is longer, of randomization (Visit 2). 
15. Other investigational product/clinical study:
 
 • Subjects who have received treatment with an investigational agent (biologic or non-biologic) within the past 30 days or 5 drug half-lives whichever is longer, prior to randomization (Visit 2). The term “investigational” applies to any drug not approved for sale in the country in which it is being used or investigational formulations of marketed products • Subjects who are currently participating in any other interventional clinical study |
|--|

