7.7. Immunogenicity

Blood samples will be collected prior to dosing at visits specified in the Time and Events Table (Section 7.1). Samples will be analysed for the presence of anti-mepolizumab antibodies.

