Concomitant meds including maintenance OCS	X	X	X	X	X	X	X	X	X	X	X	X	X	X	X	
Vital signs 		X	X		X	X	X	X	X	X	X	X	X		X	
ECG		X										X	X			
AEs			X	X	X	X	X	X	X	X	X	X	X	X	X	X
SAEs		X	X	X	X	X	X	X	X	X	X	X	X	X	X	X
Laboratory assessments																
Hematology 		X	X	X	X	X	X	X	X	X	X	X	X	X	X	X 

CONFIDENTIAL

200622

Procedures	Pre-screen	Screen	Randomization	Double-blinded treatment period												Additional follow-up
Chemistry 		X			X	X	X	X	X	X	X	X	X	X	X 	X 
Troponin		X			X	X	X	X	X	X	X	X	X	X	X 	X 
Pregnancy test 		X	X		X	X	X	X	X	X	X	X	X		X 	X 
Aldolase		X			X	X	X	X	X	X	X	X	X			
Lipoproteins (fasting) 		X														
Urinalysis 		X										X		X 	X 	
Hep B & C serology 		X														
F/P status 		X														
T-cell profile		X										X		X 	X 	
Total IgE			X													

Procedures	Pre-screen	Screen	Randomization	Double-blinded treatment period												Additional follow-up
				3	4	5	6	7	8	9	10	11 End-of-treatment	Flare 	3-11 for subjects who prematurely discontinue study treatment 	EW	
Study visit	0	1	2	3	4	5	6	7	8	9	10	11 End-of-treatment	Flare 	3-11 for subjects who prematurely discontinue study treatment 	EW	12
Study week		Up to ~4 weeks (wks)	0	2 (± 5 days)	4 ±1 wks	8 ±1 wks	12 ±1 wks	16 ±1 wks	20 ±1 wks	24 ±1 wks	28 ±1 wks	32 ±1 wks				~12 wks after last dose ±1 wks
PK					X			X				X		X 	X 	X 
PD (IL-5)			X									X	X			
Immunogenicity (Anti-drug antibody)			X					X				X		X 	X 	X 
Genetics 			X													
Sample collection for biomarker sub-study 			X									X	X	X 	X 	
Investigational product & other study treatment																

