**16.6.3. Study Population**

Age

 
• GSK standard IDSL algorithms will be used for calculating age where birth day and month will be imputed 'PPD'
 
• Birth date will be presented in listings as 'YYYY'.
 
• Age will be calculated relative to the date of the screening visit (Visit 1).
 

Body Mass Index (BMI)
Calculated as Weight (kg) / [Height (m)]
Baseline HES Therapy

 
• Baseline oral corticosteroid use and baseline oral prednisone equivalent daily dose will be derived as detailed in Section 5.4.1.1.
 
• Cytotoxic therapy/immunosuppressive therapy and other HES therapy will be identified by clinical review of the concomitant medications page according to the following criteria:             
 
○ Medication type = "Hypereosinophilic syndrome"
 
○ Start date < Date of first dose of study treatment
 
○ Either "ongoing" or End date ≥ Date of first dose of study treatment
 
 
 
• Oral budesonide has negligible systemic exposure and will be counted as "Other HES therapy" rather than oral corticosteroid therapy.
 

Duration of HES

 
• Duration of HES in years will be calculated from the date of the screening visit (Visit 1) and the date of HES diagnosis as follows: Duration (years) = (Date of visit 1 – date of HES diagnosis)/365.25
 
• If the date of HES diagnosis is a partial date, a '01' will be used for a missing day and 'Jan' will be used for a missing month.
 

Exposure (therapeutic coverage)

 
• The number of days of exposure (therapeutic coverage) to study drug will be calculated based on the formula: Duration of exposure in days = Date of last dose of study treatment – date of first dose of study treatment + 29.
 
• Exposure in months will be calculated using the formula: Exposure (months) = (Exposure in days / 365.25) * 12
 
• Total subject years exposure will be calculated using the formula: Total subject-years exposure = (Sum across subjects of exposure in days)/365.25
 

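### SAP 12.1: the transient and persistent antibody categories still count the pre-dose Week 0 sample, because the only visit left out is one at which no antibody sample is taken

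*SAP*

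**What the plan says.** SAP 12.1 gives the categories for the binding antibody results. Persistent positive can be reached in two ways: a confirmed positive "for at least 2 consecutive assessments excluding the screening visit", "or a single result at the final study assessment". Transient positive is "a single confirmatory positive immunogenic response that does not occur at the final study assessment". The first definition names one visit to leave out; the second names none.

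The sampling times are in the schedule (Protocol Table 2, repeated in SAP 16.2.1). The antibody row is marked at Visit 2 (Week 0), Visit 7 (Week 16) and Visit 11 (Week 32), and in the columns for early discontinuation of treatment, early withdrawal and Visit 12. The Visit 1 (screening) cell is empty. On timing, Protocol 7.7 states: "Blood samples will be collected prior to dosing at visits specified in the Time and Events Table". The Week 0 sample is therefore taken before any study treatment.

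The same definitions stand in both SAP versions supplied, February 2019 and the June 2019 amendment.

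**The concern.** A rule for persistence normally sets aside the pre-treatment sample, so that the category describes what happens after dosing starts. The exclusion in 12.1 appears to have that purpose but names a visit without a sample. The one pre-dose result that exists then stays in the persistent rule as one of the two consecutive positives. It also stays in the transient rule, for a different reason: that rule has no exclusion at all.

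Pre-dose positives are possible in this trial. Exclusion criterion 13 in Protocol 5.2 bars mepolizumab only during the 4 months before randomization, so earlier exposure is allowed. The SAP itself foresees them, since it plans a separate summary for subjects with no positive result before dosing (Table 4.61). Immunogenicity is a listed safety endpoint. What is at stake is that antibody already present before randomized treatment would be reported, in either arm, as transient or persistent positivity.

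**Working it through.** The plan states no figure for this point, so there is none to reproduce. The check is a reading of the schedule followed by an enumeration of result patterns.

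**Step 1: which visit is excluded.** SAP 5.2 and SAP 16.6.3 (derivation of age) both identify the screening visit as Visit 1. Matching the antibody row to the 17 columns of the schedule puts marks under Visits 2, 7 and 11 and the discontinuation, early withdrawal and Visit 12 columns. Visit 1 has none, so excluding it removes no result.

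**Step 2: apply the rule to every pattern that is positive at Week 0.** The rule as coded:

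- no positive: negative
- two adjacent positives, or a positive at the last assessment: persistent
- exactly one positive, not the last: transient
- anything else: fits no category

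The right-hand column applies the same rule after deleting Week 0.

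Three samples (Weeks 0, 16, 32):

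| W0 | W16 | W32 | As written | Week 0 excluded |
|---|---|---|---|---|
| + | − | − | transient | **negative** |
| + | − | + | persistent | persistent |
| + | + | − | persistent | **transient** |
| + | + | + | persistent | persistent |

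Two of 4 change. With a fourth sample at Visit 12, 3 of 8 change:

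| W0 | W16 | W32 | V12 | As written | Week 0 excluded |
|---|---|---|---|---|---|
| + | − | − | − | transient | **negative** |
| + | + | − | − | persistent | **transient** |
| + | − | + | − | fits no category | **transient** |

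The other five Week 0-positive patterns are persistent either way. Patterns negative at Week 0 never change, so the totals are 2 of 8 and 3 of 16 over all patterns. These are counts of patterns, not of patients.

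**Step 3: which outputs are touched.** Three outputs already leave Week 0 out:

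- the highest post-baseline binding result (SAP 12.1, also requested within Table 4.60)
- adverse events by that result (Table 4.10)
- the treatment-emergent summary (Table 4.61), restricted to subjects without a pre-dose positive and to visits after Week 0

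Only the transient/persistent split remains exposed.

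**The case against.** The best defence is that the intent is clear. The SAP uses screening loosely for baseline elsewhere: the blood eosinophil model in 10.1.5.1 puts the word in parentheses after baseline and reports a ratio to screening, although baseline there is the last central value before the first dose. On that reading the persistent rule already works. This has some force, but it is not enough. Section 12.1 has its own terms for the pre-dose concept (post-baseline, before dosing) and does not use them here. It also uses screening for the first assay tier. Even on the charitable reading the transient rule still counts Week 0.

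The other objections limit the point, and they stand. A reader might infer any of the following, and the documents support none of them:

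- **That on-treatment or treatment-emergent positivity is misreported.** SAP 12.1 never labels the transient and persistent categories as on-treatment. Its treatment-emergent summary is separate and already protected.
- **That Table 4.60 demonstrably carries the wrong categories.** The display list gives only its title, shell code and a note. The shells are not in the documents. As a by-visit table it may well show Week 0 separately already.
- **That the size can be taken from the 6% antibody rate in Protocol 4.6.1.** Applied to 40 subjects this gives 0.06 × 40 = 2.4. But the 6% is incidence in severe asthma at 100 mg SC. It is not pre-dose prevalence, not HES and not 300 mg, and it is not split by category. It says nothing about how many subjects would be misclassified here.

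**Conclusion.** Wrong as written, and minor. The exclusion in the persistent definition has no effect, and the transient definition has none. A subject with antibody only before treatment is called transient positive. A subject with one post-dose positive that follows a positive Week 0 is called persistent positive even if all later samples are negative.

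The effect is limited to subjects positive at Week 0 and to the transient/persistent categories. No hypothesis test, treatment-emergent result or adverse-event-by-antibody table is affected. The number of subjects cannot be given: the documents state no baseline antibody prevalence for this population, and exclusion 13 shows only that pre-dose antibody is possible. The conclusion assumes that the screening visit means Visit 1, as the SAP uses it in 5.2 and 16.6.3. If it was meant as the pre-dose baseline, the fault in the transient definition remains.

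**What to change.** In SAP 12.1:

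1. In the persistent definition, replace the exclusion of the screening visit with exclusion of the pre-dose Week 0 (Visit 2) assessment.
2. Apply the same exclusion to the transient definition, so that both use post-dose samples only.
3. State that Week 0 results are reported simply as positive or negative at baseline. The section categorises results at each visit, so it must say how Week 0 is labelled.
4. Assign a category to two or more non-consecutive post-dose positives that do not include the final assessment. With Week 0 removed, the schedule gives at most three post-dose samples, and two separated positives among three must include the last. This rule therefore matters only if a subject has additional samples, but it closes the definition.

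The cost is a short SAP edit and a small change to the derivation. No new sample, assay or data collection is needed.

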## **13. PHARMACOKINETIC / PHARMACODYNAMIC ANALYSES**

In support of the analysis described below, a specific dataset will be generated. Specifications for the generation of the dataset will be provided in a separate document.

The details of the planned displays are presented in [Appendix 10](#): List of Data Displays.

### **13.1. Population of Interest**

The population PKPD analysis will be performed on the PK and PD populations.

### **13.2. Strategy for Intercurrent (Post-Randomization) Events**

For subjects withdrawing prematurely from study treatment, all available data will be included in the analysis.

Zero values for the baseline blood eosinophil count as well as for blood eosinophil count will be replaced by half of the lowest observed detectable (non-zero) value in the study data set (consistent with approaches used in other analyses).

Outlier data will be assessed for plausibility, however the aim is to use all available data whenever possible. Any decision to exclude data will be fully documented and specified in the clinical study report.

### **13.3. Population Pharmacokinetic/Pharmacodynamic Methodology**

If deemed appropriate, a population pharmacokinetic/pharmacodynamic analysis will be conducted.

Blood eosinophil count were measured during the course of the study over the 32 weeks treatment period and will be analysed by population methods using the most recent population PKPD model (meta-analysis PKPD model of data across indications described in GlaxoSmithKline Document Number [2015N238436\\_00](#)).

The objectives of the population PKPD analysis are:

- To evaluate mepolizumab pharmacodynamics in subjects with HES following subcutaneous administration of a 300 mg dose every 4 weeks;
- To investigate the impact of covariates of interest in the studied HES population (such as baseline characteristics, co-medication) on specific parameters (e.g. maximum blood eosinophil reduction) in order to identify potential sources of inter-individual variability in these parameters.

Mepolizumab blood eosinophil count-time data (samples collected at screening, Week 2, Week 4 and every 4 weeks for the remainder of the 32-week treatment period) will be analysed by population methods using nonlinear mixed-effects modelling. The analysis will be carried out using appropriate software (e.g., NONMEM or SAS).

### 13.3.1. Base Model

The most recent population PKPD model will be applied directly to the dataset without estimation (e.g. maxevals=0 in NONMEM) and predictions generated against which the model will be validated prospectively using appropriate goodness of fit tests as described in Section 9.3.1 (using the observed data from the study).

The following will be obtained:

- A description of the key models tested during the model development will be provided and tabulated.
- The population PD parameter estimates with 95% CI from the final model will be tabulated. Goodness of fit plots for the final model will be presented.

The most recent population PKPD model consists of an indirect response model parameterised in term of baseline blood eosinophil count (KRO), rate of elimination of eosinophils in the blood (Kout), concentration resulting in 50% of maximum drug effect (IC50) and maximum effect (Imax). Observed baseline blood eosinophil count is included as covariates of both predicted baseline and mepolizumab inhibitory response; and disease for predicted baseline blood eosinophil count. Details of the model can be found in GlaxoSmithKline Document Number [2015N238436\\_00](#) and GlaxoSmithKline Document Number [2015N255079\\_00](#) (extension of the former report).

### 13.3.2. Investigation of Covariates

The impact of the following prospectively selected plausible covariates on relevant parameters (i.e., baseline blood eosinophil count and maximum effect) will be evaluated.

Category	Covariates
Demographics	Age, race, gender
Baseline disease status	Flare history, blood eosinophils (already included in the current model)
Others	Baseline OCS absolute dose, presence/absence of anti-drug antibodies*, immunosuppressant therapies* (e.g. methotrexate, azathioprine and mycophenolate mofetil), interferon alfa*

\*Attempt to investigate those covariates will be made providing data permits.

Covariate selection will be based on physiological plausibility, supported by graphical evaluation (PD parameters vs. covariates), and formally by automated linear model fitting using proc glmselect in SAS 9.2 (or higher). Individual PD parameters and covariates will be log-transformed and standardized before analysis. For forward and backward selections, significance levels of 0.1 and 0.05 will be applied respectively, in line with criteria used in previous analyses. Co-linearity between covariates will be carefully considered.

Identified covariates will then be subjected to traditional covariate analysis (with estimation step) and will follow the same procedures as described in Section 9.3.3 for the population PK model.

Model evaluation will be as described in Section 9.3.4 for the population PK model.

